6.2. Safety Variables

6.2.1. Adverse Events

Adverse events will be organized in 2 different ways: by event and by subject. The by event dataset will include all the characteristics of the event obtained on the eCRF plus the derived variables presented in Table 12. A second by event dataset will be created for the AE duration analysis. This duration dataset will contain only the subject number, treatment session, body system classification, preferred term, and duration.

Variable	Values/Definition
Treatment-Emergent	AE with a start date after the first dose of study medication
QWO-Related	If relationship to QWO (CCH-aaes) is reported as possible, probable or missing; 'unlikely related' AE will be classified as not a drug-related AE.
Mitigation-Related	If relationship to study mitigation only is reported as possible, probable or missing; 'unlikely related' AE will be classified as not a mitigation-related AE.
Onset Day	AE Start Date - Date of First Injection + 1
Duration	AE Stop Date - AE Start Date + 1

Table 12:Adverse Event Variables by Event

AE=Adverse event

The by-subject dataset will summarize all the AE events for a subject and will include the variables presented in Table 13. The same variables will be computed for TEAEs and treatment-related AEs.

Table 13:Adverse Event Variables by Subject

Variable	Values/Definition
Total AEs	Sum of number of AEs the subject reported
Total Mild AEs	Sum of number of mild AEs the subject reported
Total Moderate AEs	Sum of number of moderate AEs the subject reported
Total Severe AEs	Sum of number of severe AEs the subject reported
Had AE	Flag (Y/N) to indicate subject had at least 1 AE
Had Severe AE	Flag (Y/N) to indicate subject had at least 1 AE of moderate or severe severity
Had SAE	Flag (Y/N) to indicate subject had at least 1 serious AE

Variable	Values/Definition
Had AE Leading to Discontinuation	Flag (Y/N) to indicate subject had at least 1 AE that led to discontinuation from the study
Had AE Leading to Interruption/Withdrawal of QWO (CCH-aaes)	Flag (Y/N) to indicate subject had at least 1 AE that led to interruption/withdrawal of QWO (CCH-aaes)
Had AE Leading to Interruption/Withdrawal of Mitigation	Flag (Y/N) to indicate subject had at least 1 AE that led to interruption/withdrawal of Mitigation treatment

 Table 13:
 Adverse Event Variables by Subject (Continued)

AE=Adverse event; SAE=Serious adverse event; Y/N=Yes/No

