Inclusion/exclusion criteria	Х								
Medical history/surgical history/cellulite history including previous treatments	Х								
Prior/concomitant medications/procedures (including all prior medications/procedures for cellulite)	х	Х	Х	Х	Х	Х	Х	Х	Х
Physical examination (including height)	Х								
Weight	Х								Х
Fitzpatrick skin type	X ^a								
Vital signs	Х	X ^b							
Digital photography ^c		Х	Х	Х	Х	Х	X ^d	X ^d	Х
Cohort assignment	X e								
QWO (CCH-aaes) administration		Х					Х	Х	
Subject Assessments									
Subject-Bruising Improvement Scale (S-BIS)			Х	Х	Х	Х	X d		
Patient Bother by Bruising Scale ^g				Х	Х		X d		
Investigator Assessments									
Hexsel Cellulite Severity Scale (CSS) Subsection D	X ^h								
Clinician-Reported Photonumeric Cellulite Severity Scale (CR-PCSS)	X ⁱ								
Selection and marking of dimples to be treated with both buttocks		X ^c					X ^d	X d	
Investigator Assessment of Bruising Severity Scale		Х	Х	Х	Х	Х	X d		
Investigator- Bruising Improvement Scale (I-BIS) ^j			Х	Х	Х	X	X ^d		
Investigator- Global Aesthetic Improvement Scale (I-GAIS)							X ^d	Х	Х

Table 2: Study EN3835-401 Schedule of Assessments

	Screening Period			Tre	atment Pe	eriod			Follow-Up Period
Procedures	Day -14	Day 1 (Baseline)	Day 2	Day 4	Day 7	Day 14	Day 22 (± 3d)	Day 43 (± 3d)	Day 71/ET (+7d)
Mitigation Treatment Cohorts	Aitigation Treatment Cohorts								
Compression garments			$X^{k,j}$)					
Instant cold packs to the right buttock only		X l,p							
Arnica patches (OcuMend [®]) to the right buttock only		X ^m ,	p						
INhance Post-Injection Serum with TriHex Technology [®] to the right buttock only			X ^{n,j})					
Pulse dye laser (PDL) treatment to the right buttock only			X ^{0,j})					
Injection site reactions/local tolerability in each buttock treated		Х	Х	Х	Х	Х	Х	Х	Х
Adverse events (AEs)						X q			

Table 2: Study EN3835-401 Assessments (Continued)

^a Subjects with a Fitzpatrick skin rating of I-III will be included.

^b Before injection and approximately 30 minutes after injection. Pulse and blood pressure should be collected after the subject has been sitting for 5 minutes.

^c Buttocks will be photographed before and after injection site and dimple marking on Days 1, 22, and 43. Buttocks will also be photographed during the Days 2,

4, 7, 14, and 71 visits (ET) (no dimple or injection site markings).

^d. Before injection.

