2.14. Vital Signs

Temperature, pulse, systolic blood pressure, and diastolic blood pressures will be collected at the Screening Visit, and before the first QWO (CCH-aaes) injection and approximately 30 minutes after injection on Day 1. Pulse and blood pressure will be collected after the subject has been sitting for 5 minutes. The investigator will review all vital sign values for clinical significance. Any vital sign value meeting the investigator's criteria for clinical significance will be recorded as an AE (or SAE, if appropriate).

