3.5. Safety Parameters

3.5.1. Adverse Events and Treatment-Emergent Adverse Events

Adverse events will be mapped to system organ class and preferred term using the Medical Dictionary for Regulatory Activities (MedDRA). Treatment-emergent adverse events (TEAEs) are any AEs with a start date equal to or after the date of the first injection of QWO (CCH-aaes).

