No Severe TEAE, but at least one Moderate TEAE	n (%)	xx (xx.x)	xx (xx.x)	 XX (XX.X)
No Severe/Moderate TEAEs, but at least one Mild TEAE	n (%)	xx (xx.x)	xx (xx.x)	 xx (xx.x)
At least one TEAE Leading to Withdrawal from Study	n (%)	xx (xx.x)	xx (xx.x)	 xx (xx.x)
At least one TEAE Leading to Interruption/Discontinuation of OWO (CCH-aaes) only	n (%)	xx (xx.x)	xx (xx.x)	 xx (xx.x)
At least one TEAE Leading Interruption/Discontinuation of Mitigation Treatment only	n (%)	xx (xx.x)	xx (xx.x)	 xx (xx.x)
At least one TEAE Leading to Interruption/Discontinuation of both QWO (CCH-aaes) and Mitigation Treatment	n (%)	xx (xx.x)	xx (xx.x)	 xx (xx.x)
Number of Subjects with TEAEs Resulting in Death	n	XX	XX	 XX

[1] Treatment emergent adverse events (TEAEs) are adverse events with a start date after the first dose of QWO (CCH-aaes). Total number of adverse events reported includes the same adverse event occurring multiple times for a subject being counted at each occurrence. Percentages were based on the overall total number of all adverse events within the cohort.

[2] Treatment emergent adverse events (TEAEs) reported as having possibly or probably related to either QWO, or mitigation treatment, or both. Missing relationships were considered as related.

Note: Safety Population includes all enrolled subjects who received at least 1 injection of QWO (CCH-aaes) with or without mitigation treatment.

Datasets (extraction): status(ddmmmyyyy), Source: ...\xxxxxx.sas

Programming note: please include columns for cohorts 1-3 on page 1, and columns for cohorts 4-6 and Overall on page 2 if it is impossible to put all columns in one page. Cohort column headers should read: "Cohort 1 No Mitigation", "Cohort 2 Compression", "Cohort 3 Cold Packs", "Cohort 4 Arnica Patches", "Cohort 5 INhance Serum", "Cohort 6 PDL Treatment".

Table 14.3.1.2 Overall Summary of QWO-Related Adverse Events Safety Population

Datasets (extraction): status(ddmmmyyyy), Source: ...\xxxxxx.sas ddmmmmyyyy:HHMM

Programming note: Use same format as Table 14.3.1.1 with QWO- Related Adverse Events only. Replace TEAE with QWO-Related AEs. Do not include rows "Related to xxx" and "At least 1 AE leading to interruption or discontinuation of xxx".

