^[1] QWO-related adverse events (QWO-related AEs) are treatment-emergent adverse events reported as having possibly or probably related to QWO (CCH-aaes). Missing relationships were considered as related. Total number of adverse events reported includes the same adverse event occurring multiple times for a subject being counted at each occurrence. Percentages were based on the overall total number of all adverse events within the cohort.

Note: Safety Population includes all enrolled subjects who received at least 1 injection of QWO (CCH-aaes) with or without mitigation treatment.

Table 14.3.1.3 Overall Summary of Mitigation-Related Adverse Events Safety Population

[1] Mitigation-related adverse events (Mitigation-related AEs) are treatment-emergent adverse events reported as having possibly or probably related to the mitigation treatment. Missing relationships were considered as related. Total number of adverse events reported includes the same adverse event occurring multiple times for a subject being counted at each occurrence. Percentages were based on the overall total number of all adverse events within the cohort.

Note: Safety Population includes all enrolled subjects who received at least 1 injection of QWO (CCH-aaes) with or without mitigation treatment.

Datasets (extraction): status(ddmmmyyyy), Source: ...\xxxxxx.sas ddmmmmyyyy:HHMM

Programming note: Use same format as Table 14.3.1.1 with Mitigation-Related Adverse Events only. Replace TEAE with Mitigation-Related AEs.. Do not include rows "Related to xxx" and "At least 1 AE leading to interruption or discontinuation of xxx".

System Organ Class Preferred Term [1]	Statistic	Cohort 1 No Mitigation (N=xxx)	Cohort 2 Compression (N=xxx)	 Cohort 6 PDL Treatment (N=xxx)
Number of Subjects with at least one TEAE [2]	n (%)	xx (xx.x)	xx (xx.x)	 xx (xx.x)
System Organ Class 1	n (%)	xx (xx.x)	xx (xx.x)	 xx (xx.x)
Preferred Term 1	n (%)	xx (xx.x)	xx (xx.x)	 xx (xx.x)
Preferred Term 2	n (%)	xx (xx.x)	xx (xx.x)	 xx (xx.x)
Preferred Term 3	n (%)	xx (xx.x)	xx (xx.x)	 xx (xx.x)
System Organ Class 2	n (%)	xx (xx.x)	xx (xx.x)	 xx (xx.x)
Preferred Term 4	n (%)	xx (xx.x)	xx (xx.x)	 xx (xx.x)
Preferred Term 5	n (%)	xx (xx.x)	xx (xx.x)	 xx (xx.x)
Preferred Term 6	n (%)	xx (xx.x)	xx (xx.x)	 xx (xx.x)
Preferred Term 7	n (%)	XX (XX.X)	xx (xx.x)	 xx (xx.x)

Table 14.3.2.1 Treatment-Emergent Adverse Events by System Organ Class and Preferred Term Safety Population

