[1] System organ class and preferred term were coded using MedDRA dictionary (Version xx.x). If multiple adverse events were reported within a given system organ class and/or preferred term, only one event was counted per subject.

[2] Treatment-emergent adverse events (TEAEs) are adverse events with a start date after the first dose of QWO (CCH-aaes).

Note: Safety Population includes all enrolled subjects who received at least 1 injection of QWO (CCH-aaes) with or without mitigation treatment.

Datasets (extraction): status(ddmmmyyyy), Source: ...\xxxxxx.sas

Programming note: please include columns for cohorts 1-3 on page 1, and columns for cohorts 4-6 and Overall on page 2 if it is impossible to put all columns in one page. Cohort column headers should read: "Cohort 1 No Mitigation", "Cohort 2 Compression", "Cohort 3 Cold Packs", "Cohort 4 Arnica Patches", "Cohort 5 INhance Serum", "Cohort 6 PDL Treatment".

Table 14.3.2.2 QWO-Related Adverse Events by System Organ Class and Preferred Term Safety Population

[1] System organ class and preferred term were coded using MedDRA dictionary (Version xx.x). If multiple adverse events were reported within a given system organ class and/or preferred term, only one event was counted per subject.

Datasets (extraction): status(ddmmmyyyy), Source: ...\xxxxxx.sas ddmmmmyyyy:HHMM

Programming note: Use same format as Table 14.3.2.1 with QWO-Related events only. Replace TEAE with QWO-Related AEs..

^[2] QWO-related adverse events (QWO-related AEs) are treatment-emergent adverse events reported as having possibly or probably related to QWO (CCH-aaes). Missing relationships were considered as related.

Note: Safety Population includes all enrolled subjects who received at least 1 injection of QWO (CCH-aaes) with or without mitigation treatment.

Table 14.3.2.3 Mitigation-Related Adverse Events by System Organ Class and Preferred Term Safety Population

[1] System organ class and preferred term were coded using MedDRA dictionary (Version xx.x). If multiple adverse events were reported within a given system organ class and/or preferred term, only one event was counted per subject.

Datasets (extraction): status(ddmmmyyyy), Source: ...\xxxxxx.sas ddmmmmyyyy:HHMM

Programming note: Use same format as Table 14.3.2.1 with Mitigation-Related events only. Replace TEAE with Mitigation-Related AEs.

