[1] System organ class and preferred term were coded using MedDRA dictionary (Version xx.x). If multiple serious adverse events were reported within a given system organ class and/or preferred term, only one event was counted per subject.

[2] Serious adverse events (SAEs) were determined by the investigator and marked as SAE on eCRF.

[3] Occurrence is the total number of times the serious adverse event was reported in the study.

Note: Safety Population includes all enrolled subjects who received at least 1 injection of QWO (CCH-aaes) with or without mitigation treatment.

Datasets (extraction): status(ddmmmyyyy), Source: ...\xxxxxx.sas

Programming note: please include columns for cohorts 1-2 on page 1, columns for cohorts 3-4 on page 2, and columns for cohorts 5-6 on page 3. Cohort column headers should read: "Cohort 1 No Mitigation", "Cohort 2 Compression", "Cohort 3 Cold Packs", "Cohort 4 Arnica Patches", "Cohort 5 INhance Serum", "Cohort 6 PDL Treatment".
		No M	ohort 1 Nitigation N=xxx)	 Cohort 6 PDL Treatment (N=xxx)
Preferred Term [1]	System Organ Class [1]	Subjects n (%)	Occurrence [3] n	
any Most Common Non-Serious TEAE [2]		xx (xx.x)	xx (xx.x)	 xx (xx.x)
Most Frequent Preferred Term	System Organ Class	xx (xx.x)	xx (xx.x)	 xx (xx.x)
2 nd Most Frequent Preferred Term	System Organ Class	xx (xx.x)	xx (xx.x)	 xx (xx.x)
3 rd Most Frequent Preferred Term	System Organ Class	xx (xx.x)	xx (xx.x)	 XX (XX.X)

Table 14.3.5.1 Summary of Most Common (>=5%) Non-Serious Treatment-Emergent Adverse Events by Frequency Safety Population

[1] System organ class and preferred term were coded using MedDRA dictionary (Version xx.x). If multiple serious adverse events were reported within a given system organ class and/or preferred term, only one event was counted per subject.

[2] Any non-serious TEAEs (adverse events with a start date after the first dose of QWO [CCH-aaes]) reported at least 5% of subjects in any cohort at least once.

[3] Occurrence is the total number of times the non-serious TEAE was reported in the study.

Note: Safety Population includes all enrolled subjects who received at least 1 injection of QWO (CCH-aaes) with or without mitigation treatment.

Datasets (extraction): status(ddmmmyyyy), Source: ...\xxxxxx.sas ddmmmmyyyy:HHMM

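### The SAP's derivation table and four shell footnotes define treatment-emergent AEs so that a literal date comparison drops every AE dated Day 1, and a separate flag counts subjects with moderate AEs as severe

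*SAP*

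**What the plan says.** The SAP gives two rules for treatment emergence.

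- **SAP 3.5.1** defines TEAEs as "any AEs with a start date equal to or after the date of the first injection of QWO (CCH-aaes").
- **SAP 6.2.1, Table 12**, the list of derived variables, defines the treatment-emergent variable as an "AE with a start date after the first dose of study medication".
- **Shell footnotes** follow Table 12. Table 14.3.1.1 has "Treatment emergent adverse events (TEAEs) are adverse events with a start date after the first dose of QWO (CCH-aaes"). Tables 14.3.2.1 and 14.3.3.1 have "Treatment-emergent adverse events (TEAEs) are adverse events with a start date after the first dose of QWO (CCH-aaes"). Table 14.3.5.1 has "adverse events with a start date after the first dose of QWO [CCH-aaes"].

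Other passages that bear on the point:

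- SAP 2.11 lists the AE items collected. They include the date of onset but no time.
- SAP 6.1 (Table 11) sets the date of the first injection to the Day 1 visit date.
- SAP 6.3 treats an AE with a missing onset day as treatment-emergent unless its month and year precede the first injection.
- Protocol 9.3.2.1 restricts all AE summaries to TEAEs.

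On severity, SAP Table 13 sets the subject flag *Had Severe AE* when the subject has any AE of moderate or severe intensity. SAP 5.8.1 and 5.8.1.1, and the shell of Table 14.3.1.1, place each subject in only one of severe, moderate or mild, by worst AE.

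**The concern.** The restrictive wording sits in the derivation table and the shells, which are what a programmer works from. The SAP sets no order of precedence between these and section 3.5.1. If the code follows Table 12, AEs dated Day 1 leave the TEAE tables. If it follows 3.5.1, four footnotes misstate the rule behind their own tables. One text is wrong either way.

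Day 1 onsets are to be expected. The schedule of assessments (SAP Table 2) includes the Day 1 visit in the row "Injection site reactions/local tolerability in each buttock treated". SAP 2.14 schedules a reading about 30 minutes after the Day 1 injection and states: "Any vital sign value meeting the investigator's criteria for clinical significance will be recorded as an AE (or SAE, if appropriate"). Under that section and the schedule, Day 1 is the only day with a post-injection reading, so an AE dated by it carries the Day 1 date.

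The endpoint at stake is the secondary safety endpoint, the percentage of subjects reporting each AE and TEAE. The severity flag raises a different risk: overstating how many subjects had a severe event.

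**Working it through.** The plan states no figure to reproduce here, so the check compares the definitions.

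**1. The two rules by date.** Let *s* be the AE start date and *d* the date of first injection. SAP 3.5.1 is *s* ≥ *d*. Table 12 compared by date is *s* > *d*. Study day follows SAP 6.4.

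| Study day of onset | SAP 3.5.1 | Table 12, literal |
|---|---|---|
| −1 | not TEAE | not TEAE |
| 1 | **TEAE** | **not TEAE** |
| 2 | TEAE | TEAE |
| 3 | TEAE | TEAE |

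The rules differ on Day 1 only. Reading *after* as clock time would remove the conflict, but no onset time is collected, so that reading cannot be programmed.

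**2. Partial dates.** Take an AE that starts on Day 1. With a complete date it fails the literal Table 12 rule. With the day missing and the same month and year, SAP 6.3 counts it as treatment-emergent. The better-documented record is the one dropped.

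**3. Spread to other tables.** The QWO-related and mitigation-related shells build on the TEAE definition. The footnote of Table 14.3.1.2, for example, reads "QWO-related adverse events (QWO-related AEs) are treatment-emergent adverse events reported as having possibly or probably related to QWO (CCH-aaes"). Six such footnotes (Tables 14.3.1.2, 14.3.1.3, 14.3.2.2, 14.3.2.3, 14.3.3.2 and 14.3.3.3) inherit the rule.

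**4. Size in a cohort of 8.** The number of subjects whose only AE under a preferred term is dated Day 1 is an assumption.

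- 1 subject: 1/8 = 12.5 points lost from that row
- 2 subjects: 2/8 = 25 points
- 4 subjects: 4/8 = 50 points

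Table 14.3.5.1 shows terms reported by at least 5% of subjects in any cohort. One subject in 8 is 12.5%, above 5%, so a term reported once belongs in the table. It would disappear if that report is dated Day 1.

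**5. Scale for bruising.** Protocol 2.1 gives 84% injection site bruising in the Phase 3 studies. Assume this applies to the first session here: 0.84 × 48 = 40.3 subjects. If 25%, 50%, 75% or 100% of those first-session AEs are dated Day 1, about 10, 20, 30 or 40 AEs drop out. The share is not in the documents. Subject-level incidence falls by less wherever bruising recurs after session 2 or 3.

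**6. Severity flag.** Take an illustrative cohort of 8: 1 subject with a severe AE, 3 with moderate as worst, 3 with mild as worst, 1 with no AE.

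- SAP 5.8.1 severe row: 1/8 = 12.5%
- Table 13 flag: (1 + 3)/8 = 50.0%
- Severe, moderate and mild rows under 5.8.1: 1 + 3 + 3 = 7, the number of subjects with an AE
- The same rows with the flag feeding the severe row: 4 + 3 + 3 = 10, although only 7 subjects have an AE

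**The case against.** The best case for leaving this alone is that the intent is clear. SAP 3.5.1 is date-based and inclusive, Protocol 10.2.1 defines a TEAE as a condition that appears following treatment, and SAP 6.3 leans the same way. A careful programmer would include Day 1. That supports 3.5.1 as the intended rule, but it does not correct the derivation table or the four footnotes.

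Several limits on reach do stand:

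- SAP 3.5.1.3, 3.5.1.4 and Table 12 define related AEs without requiring treatment emergence. The spread to the related-AE tables therefore rests on the shell footnotes and on Protocol 9.3.2.1.
- SAP 5.8.1 draws the listings of deaths and non-fatal SAEs from all AEs. Day 1 events also remain in Listing 16.2.7.1, though its TEAE column would mark them as not treatment-emergent.
- With three sessions, a subject with a later AE under the same term still counts.
- The 12.5, 25 and 50 point figures are fractions of 8, not estimates. Nothing shows that AEs from vital signs are likely.
- SAP 5.8.3 mentions a pre-injection baseline at each session, but SAP 2.14, SAP 3.5.2 and the schedule provide for Day 1 only.
- No text feeds the Table 13 flag into a table. It acts per subject, and the counts of moderate and severe AEs in Table 13 are correct. SAP 3.5.1.2 only lists the three grades; the direct conflict is with 5.8.1 and 5.8.1.1.

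One further point is useful: an inclusive date rule also captures an AE that began on Day 1 before the injection, which Protocol 10.2.1 would not count unless it later worsened or recurred.

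**Conclusion.** The concern holds and should be fixed. Table 12 and four footnotes contradict SAP 3.5.1, and with dates only, a literal comparison excludes every AE dated Day 1 from the TEAE summaries. The overall loss is unknown. Per preferred term it is 12.5 points in a cohort of 8 for each subject whose only AE under that term is dated Day 1. This assumes that the code follows Table 12 and not 3.5.1.

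The severity flag is also wrong as defined. It overstates the severe row by 12.5 points for each subject whose worst AE is moderate, but only if that row is programmed from the flag. The Day 4 primary endpoint and the other bruising scales do not use either variable.

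**What to change.** 1. In Table 12 and in the TEAE footnotes of Tables 14.3.1.1, 14.3.2.1, 14.3.3.1 and 14.3.5.1, state the 3.5.1 rule: start date on or after the date of the first QWO injection. The six related-AE footnotes then follow without change.
2. Add a sentence on AEs that begin on Day 1 before the injection. Counting all Day 1 onsets as treatment-emergent by convention needs no new data. Separating them would need a before/after-injection item on the AE form.
3. In Table 13, define *Had Severe AE* as at least one AE of severe intensity. Alternatively, rename it as a moderate-or-severe flag and state that it does not feed the severe-TEAE row of Table 14.3.1.1.

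Items 1 and 3, and item 2 by convention, cost SAP and shell wording only.

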6.3. Imputation of Partial Dates

Study visit dates, birthdates, informed consent date, injection dates/times, all assessment dates, and date of completion/last contact date must be complete dates; no imputations will be done. No imputations will be done for partial medical history onset/resolution dates, partial alcohol/tobacco stop dates, missing date of last menstrual period, partial AEs onset/end dates and partial concomitant medication/procedure start/stop dates. All AEs with a missing onset day will be considered treatment-emergent except if the onset month/year is prior to the first injection date. All medications/procedures with a missing onset and stop day will be considered concomitant except if the stop month/year is prior to the first injection date.

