5.4. Screen Failures

Screen failures are defined as subjects who consent to participate in this study but do not subsequently receive an injection of QWO (CCH-aaes). Screening procedures will be conducted on Day -14, prior to receiving QWO (CCH-aaes) injection. If mitigation treatments could not be procured within the 14-day Screening Period, subjects can be rescreened after the Screening Period.

Subjects who do not meet all of the eligibility criteria will be deemed a screen failure and the following information must be recorded for all subjects who are screen failures:

- Demography (age, gender, race/ethnicity).
- Reason for screen failure.
- Which eligibility criterion was not met.
- Any AEs (including serious adverse events [SAEs]) experienced by the subject.

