10.2.1. Definitions

An AE is any unfavorable or unintended change in body structure (signs), body function (symptoms), laboratory result (eg, chemistry, electrocardiogram, X-ray, etc), or worsening of a pre-existing condition associated temporally with the use of the study treatment (QWO [CCH-aaes]) or mitigation treatments) whether or not considered related to the study treatment. AEs will be captured once a subject has signed the informed consent. AEs include:

- Changes in the general condition of the subject.
- Subjective symptoms offered by or elicited from the subject.
- Objective signs observed by the investigator or other study personnel.
- All concurrent diseases that occur after the start of the study, including any change in severity or frequency of pre-existing disease.
- All clinically relevant laboratory abnormalities or physical findings that occur during the study.

A TEAE is any condition that was not present prior to treatment with study treatment but appeared following treatment, was present at treatment initiation but worsened during treatment, or was present at treatment initiation but resolved and then reappeared while the individual was on treatment (regardless of the intensity of the AE when the treatment was initiated).

An SAE is defined as an AE that:

- Results in death.
- Is immediately life-threatening (there is an immediate risk of death from the AE as it occurred; this does not include an AE that had it occurred in a more serious form may have caused death).
- Results in or prolongs an inpatient hospitalization (Note: a hospitalization for elective or preplanned surgery, procedure, or drug therapy does not constitute an SAE).
- Results in permanent or substantial disability (permanent or substantial disruption of one's ability to conduct normal life functions).
- Is a congenital anomaly/birth defect (in offspring of a subject using the study treatment regardless of time to diagnosis).
- Is considered an important medical event.

Important medical events are defined as events that, based upon appropriate medical judgment, may jeopardize the subject and may require medical or surgical intervention to prevent one of the other serious outcomes. Examples of important medical events include any cancer, allergic bronchospasm requiring intensive treatment in an emergency room or at home, blood dyscrasias or convulsions that do not result in inpatient hospitalization, or the development of drug dependency or drug abuse.

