^e Subjects will be assigned to 1 of 6 cohorts according to a site specific Mitigation Treatment Assignment Table. Cohort 1 = no mitigation treatment;

Cohorts 2-6 = mitigation treatments

^f Before QWO (CCH-aaes) injection, and 5 and 15 minutes after injection.

^gUsing mirrors, or photographs captured either by the subject or another person with the subject's imaging device (ie, cell phone, digital camera), or images captured by the investigator or designee using the site's digital photography system.

^h Baseline Hexsel CSS Subsection D must be '0' (absence of flaccidity or sagging skin) or '1' (slightly draped appearance) on each buttock.

ⁱ Baseline CR-PCSS rating must be a '3' (moderate) on each buttock.

^j Based on live assessments while the subject is in front of the investigator.

^k Compression garments will be worn after QWO (CCH-aaes) injection on Day 1 and worn 24 hours a day for the next 7 days.

¹Apply instant cold packs immediately after QWO (CCH-aaes) injection for 5-10 minutes immediately after CCH-aaes injection while subject is in a prone position.

^m Arnica patches applied BID for 2 days immediately after QWO (CCH-aaes) injection on Day 1.

ⁿ Inhance Post-Injection Serum is applied QID directly on and around the injections site for up to 7 days after QWO (CCH-aaes) injection on Day 1, until resolution of bruising.

• PDL treatment between Days 1 (same day of QWO [CCH-aaes] injection) and Day 7 after QWO (CCH-aaes) treatment. PDL settings are according to the investigator's discretion.

^p For the second and third QWO (CCH-aaes) treatment sessions, at the investigator's discretion, subjects will be allowed to use the same mitigation treatment in

the same buttock (as applicable) that received mitigation treatment for the first CCH-aaes treatment session.

^q AEs will be collected from the time the subject signed the ICF until end of the study or early termination.

BID = twice daily, d = Days, ET = early termination, ICF = informed consent form, QID = Four times daily

Endo Pharmaceuticals Inc.

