2.11. Adverse Events

Adverse Events (AEs), including both observed or volunteered problems, complaints, signs or symptoms must be recorded, regardless of whether associated with the use of study treatment. Study treatment includes QWO (CCH-aaes) and mitigation treatments.

The following information will be collected for all AEs:

- Verbatim description
- Injection Site Reaction (Yes/No)
- Date of Onset

- Date of Resolution/or Ongoing
- Severity (Mild, Moderate, Severe)
- Relationship to QWO (CCH-aaes) (Not Related, Unlikely Related, Possibly Related, Probably Related)
- Action taken with QWO (CCH-aaes) (None, Interrupted, Withdrawn)
- Relationship to Mitigation Treatment (Not Related, Unlikely Related, Possibly Related, Probably Related)
- Action taken with Mitigation Treatment (None, Interrupted, Withdrawn)
- Outcome (Recovered/Resolved, Recovered/Resolved w/Sequelae, Recovering/ Resolving, Not Recovered/Not Resolved, Fatal, Unknown)
- Whether or not a concomitant medication or procedure was required
- Classified as a serious adverse event (SAE) or not
- SAE Code (Death, Life-threatening, Inpatient or prolonged hospitalization, Persistent or significant disability/incapacity, Congenital anomaly or birth defect, Other medically important event)

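### SAP 6.3 ignores the stop date when an AE's onset day is missing, so an AE known to have ended before the first injection can be counted as treatment-emergent

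*SAP*

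**What the plan says.** SAP 6.3 (Imputation of Partial Dates) sets the rule: "All AEs with a missing onset day will be considered treatment-emergent except if the onset month/year is prior to the first injection date". The same section says that no imputation will be done for "partial AEs onset/end dates and partial concomitant medication/procedure start/stop dates", so no imputed date can later override the flag.

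Protocol 10.2.1 gives the meaning of the flag: "A TEAE is any condition that was not present prior to treatment with study treatment but appeared following treatment". Its other two routes need a condition that was present when treatment began and then either worsened, or resolved and came back. SAP 3.5.1 puts this in terms of dates: the start date must be on or after the first QWO injection. SAP Table 12 says after the first dose.

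SAP Table 2, footnote q, opens the collection period before treatment: "AEs will be collected from the time the subject signed the ICF until end of the study or early termination". Protocol 5.4 gives the length of that period: "Screening procedures will be conducted on Day -14, prior to receiving QWO (CCH-aaes) injection". Among the AE fields in SAP 2.11 is "Date of Resolution/or Ongoing", so the end of an AE is recorded even when its onset day is not.

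**The concern.** Treating an unknown onset as treatment-emergent is a sensible default. The difficulty is that a stop date before the first injection settles the matter: an event that ended before injection also began before it. The rule has no clause that uses this information, and no other section of the SAP removes such an event. The flag then contradicts the definition it is meant to implement.

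At stake is the content of the AE tables. Protocol 9.3.2.1 confines the AE summaries to TEAEs, and the SAP table shells for related AEs also start from treatment-emergent events, so this flag decides what is tabulated. The percentage of subjects with each AE and each TEAE is listed as a secondary endpoint (Protocol 3.1). With about 8 subjects per cohort, one record can visibly move a percentage.

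**Working it through.** The plan gives no figure on this point to reproduce. The check applies the rule as written and then counts dates.

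**Inputs from the documents**
- Rule (SAP 6.3): with onset day missing, the AE is not a TEAE only if its onset month/year is earlier than the month/year of the first injection.
- Pre-injection window: 14 days (Protocol 5.4 and the schedule of assessments).
- Cohort size: about 8 (SAP 8).

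**Assumptions not in the documents**
- Injection dates are uniform over the 365 days of 2021.
- Every pair of onset (1 to 14 days before injection) and stop day (onset day to the day before injection) is equally likely.

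**Step 1: the rule on four cases, first injection 20 March 2021, onset day missing**
- Onset March, stopped 12 March: flagged TEAE. This is wrong, since it ended 8 days before injection.
- Onset February, stopped 12 March: not a TEAE. Correct.
- Onset March, stopped 25 March: flagged TEAE. A reasonable default.
- Onset March, ongoing: flagged TEAE. A reasonable default.

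The error therefore needs an onset month equal to the injection month and a stop date before injection. It also arises if the onset month is missing too, because the exception then cannot be applied. The first case fails both SAP 3.5.1 and Table 12, so the result does not depend on how those two treat the injection day itself.

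**Step 2: how often a pre-injection AE would be caught**

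An onset k days before injection falls in an earlier month only when the injection is on one of the first k days of a month, which is 12k of 365 dates. The same-month share is 1 − 12k/365:
- k = 1: 1 − 12/365 = 0.967
- k = 7: 1 − 84/365 = 0.770
- k = 14: 1 − 168/365 = 0.540

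An AE with onset k days before injection that also ended before injection has k possible stop days, so earlier onsets carry more weight. The weighted mean of k over 1 to 14 is Σk²/Σk = 1015/105 = 9.67. The share flagged is 1 − 12 × 9.67/365 = 1 − 116/365 = 0.682.

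Direct enumeration of all 365 × 105 = 38,325 combinations also gives 0.682. With a stop-date exclusion added to the rule, the share is 0. In Step 1 the first case then becomes not a TEAE, and the other three are unchanged.

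**Step 3: effect of one record**

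1/8 = 12.5 percentage points. This is a maximum, because SAP 5.8.1.1 counts a subject once per preferred term. The record adds nothing if the same subject has a genuine TEAE with that term.

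**The case against.** The strongest reply is that this is a conservative rule for a rare case. Several things must coincide: onset after consent and before injection, resolution before injection, a recorded stop date, an unknown onset day, and onset in the injection month. Conditions that predate screening go to medical history (Protocol 10.2.4.1). Subjects are asked at each visit about AEs since the last one (Protocol 8.4.2), so recall is short. The error can only over-count, which fits the SAP's worst-case handling of missing severity and causality. The AE analysis is descriptive, and Listing 16.2.7.1 shows the start date, stop date and TEAE flag of every AE, so a misflagged record would be visible.

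All of that stands as to size and direction. It does not rescue the rule. A worst-case default is for what is unknown, and here the stop date makes the answer known. A programmer who follows the text reproduces the error, and one who corrects it departs from the SAP.

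Three stronger readings are tempting, and the documents do not support them.
- A reader might infer that the medication sentence, "will be considered concomitant except if the stop month/year is prior to the first injection date", shows SAP 6.3 to be inconsistent. It does not. SAP 3.6.2 defines a concomitant medication by its stop date and SAP 3.5.1 defines a TEAE by its start date, so each partial-date rule follows its own definition. The medication sentence also compares months only, so a drug stopped earlier in the injection month still counts as concomitant.
- A reader might infer that the whole safety endpoint is distorted. The endpoint covers AEs and TEAEs, and a pre-injection AE belongs in the AE part.
- A reader might infer that these records would also enter the QWO-related and mitigation-related tables. Under SAP 3.5.1.3 and 3.5.1.4 that happens by default only if causality is blank as well, and nothing in the documents suggests that this is likely.

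**Conclusion.** The point holds as a drafting error of small expected effect. Applied as written, SAP 6.3 gives a wrong flag to an AE with onset in the injection month, onset day missing, and a known stop date before the first injection.

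Under the uniform-date assumption and a 14-day window, about 68% of AEs that ended before injection and lack an onset day would be misflagged. A reader might take the figure to be three quarters. That is the average for all onsets 1 to 14 days before injection, whether or not the AE had ended: mean k is 7.5, and 1 − 12 × 7.5/365 = 0.753. It is the wrong population for this question. The existence of the error depends on neither figure.

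The number of such records is not given and should be small. Each moves a term by at most 12.5 points in a cohort of 8, always upward, and only in TEAE-based results.

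**What to change.** Replace the AE sentence in SAP 6.3 with a rule to this effect:

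> An AE whose onset day is missing is flagged treatment-emergent unless (i) its onset month/year is earlier than the month/year of the first injection, or (ii) its stop date is before the first injection date or, where the stop day is missing, its stop month/year is earlier than the month/year of the first injection.

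This keeps the present default for onsets that are truly unknown and makes the month-against-month comparison explicit. The partial-stop part of (ii) matters only when the onset month is missing too. If the onset month is known and the stop month precedes the injection month, the onset month does as well, and (i) already applies.

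The cost is one clause in the SAP and one condition in the AE derivation program. No new data are needed.
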